5 STUDY DRUG

5.1 Study Drug Treatment and Dosing

For the single-blind, run-in period, subjects will be dispensed a single-blind kit at Visit 1 (Screening). Eligible subjects will receive a double-blind study drug kit at Visit 2, Day 1 (Baseline). Thereafter, at scheduled visits (every 4 weeks through Week 8 during the double-blind treatment phase) subjects will receive 1 kit. At Week 12, subjects will receive 3 kits.

If subject cannot complete the EOS CT scan at Week 24, study staff should not complete Visit 6 in IWRS. Subjects should continue study treatment until an EOS CT scan can be completed, study staff will dispense additional study treatment via the “Unscheduled Visit” functionality in IWRS. IWRS will be contacted for each “Unscheduled Visit,” at which time one treatment kit will be dispensed.

The IWRS will assign study drug kit numbers as described in Section 3.3. Study drug packaging is described in Section 5.3.

As shown in Table 1, the study drug dosage during the double-blind treatment phase will be 186 or 372 µg of OPN-375 BID or placebo BID.

Table 1: Study Drug Dosing – Double-blind Treatment Phase

Time Bottle	OPN-375 Dosage								Placebo BID			
	186 µg BID				372 µg BID				AM		PM	
	AM		PM		AM		PM		1	2	1	2
Left nostril	PBO	93	PBO	93	93	93	93	93	PBO	PBO	PBO	PBO
Right nostril	PBO	93	PBO	93	93	93	93	93	PBO	PBO	PBO	PBO

BID=twice a day; AM=morning; PBO=placebo; PM=evening.

Throughout the study, subjects will be instructed to shake the study drug before use. They will also be instructed that it is only necessary to prime each unit before it is used for the first time as follows:

- To prime study drug, shake then actuate and spray into the air 7 times or until a fine mist appears. Note that it is not necessary to prime before every administration when it is being used regularly each day.

During the single-blind run-in and the double-blind treatment phases, the same dosing procedure will be followed for both the AM and PM doses on each day. The study staff will instruct the subject that before the AM and PM doses on each day, they will pick up the unit marked 1, shake it, then administer 1 spray to the right nostril followed by 1 spray to the left nostril, and then to pick up the unit marked 2 and repeat the same procedure.

The first dose of double-blind study drug should be administered in the PM on the day of randomization. Throughout the study, subjects will be instructed to administer study drug approximately every 12 hours. If a subject misses a dose, the dose should be taken as soon as remembered, but not within 2 hours of the next scheduled dose. In such cases the subject should wait until the next scheduled dosing time to administer a dose.

The study staff will instruct subjects to report study drug they perceive to be broken or malfunctioning and to return to the study site for evaluation and identification of the problem.

An instruction sheet on the use of study drug will be provided by the Sponsor or their designee to be given to the subjects.

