- ^a All visits up to Visit 6 (Week 24) should be scheduled based on the date of the Day 1 visit. If necessary, visits may be performed within the time window shown; however, subsequent visits should be scheduled based on the date of the Day 1 visit.
- ^b The assignment of a kit number for the demonstrator model EDS is not performed by IWRS, rather, the study staff will dispense a demonstrator model EDS kit and record the kit number in the drug dispensing log. This practice EDS is only used at the site at Visit 1 (Screening) and is not to be sent home with the subject.
- ^c Women of child-bearing potential only; urine pregnancy tests will be performed at each visit, not including subject contacts. Subjects continuing treatment past Week 24/Visit 6 will need an additional pregnancy test completed upon returning to site.
- ^d Nasoendoscopy will be performed using a rigid or flexible endoscope. The examiner must be able to visualize the middle meatus with the scope. Decongestants and/or local anesthetics may be used for the nasoendoscopic procedure.
- ^e The CT scan should be performed after diary eligibility is confirmed and prior to Day 21 of the screening run-in period.
- ^f For the Week 24 study visit, the CT examination should be performed prior to the on-site visit.
- ^g Demonstrator model EDS kit (see footnote b) and single-blind placebo dispensation only.
- ^h At Visit 1 (Screening), the IWRS will be contacted to obtain the subject ID number, the identifier for the single-blind kit to be dispensed and to track enrollment. IWRS will be contacted at Visit 2 to randomly assign subjects to treatment. At Visit 2 through – Visit 5, IWRS will be used to assign the study

drug kit(s) to be dispensed. If a subject cannot complete the EOS CT scan at Visit 6 (Week 24), study staff should not complete Visit 6 in IWRS. Subjects should continue study treatment until an EOS CT scan can be completed. Study staff will dispense additional study medication via the “Unscheduled Visit” functionality in IWRS. IWRS will be contacted for each ‘Unscheduled Visit,’ at which time one treatment kit will be dispensed.

- i The period of observation for collection of AEs extends from the time the subject gives informed consent until completion of the double-blind treatment period or an early termination visit. Serious adverse events will be reported through 30 days after the last dose of study drug administration.

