5.2 Clinical Supplies

The fluticasone propionate suspension formulation is a milky, pale, white liquid contained within an EDS. Each actuation delivers 93 µg of fluticasone propionate through the sealing nosepiece. Once primed, study drug contains not less than 120 metered sprays.

The placebo used in this investigation will be a formulation identical to the active with the omission of the drug substance fluticasone propionate and will be delivered by an identical delivery system to the active formulation.

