5.3 Packaging and Labeling

The practice EDS is to be used only at Visit 1 (Screening) to confirm a subject's ability to use the EDS and will be packaged in a demonstrator model EDS kit containing 1 unit.

Study drug will be packaged identically for each unit of study drug and placebo, and each study drug kit, including the single-blind kit, and will consist of 2 units, 1 marked "1" and 1 marked "2"; each unit will contain either 120 sprays of study drug or placebo as necessary to maintain the blind.

Labeling will contain all information required by local regulations.

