5.7 Treatment Compliance

At each visit after Visit 1 (Screening), subjects will be instructed to bring their partially used/empty study drug units back to the study site at each study visit where it will be visually inspected. At each study visit, all subjects will be reminded of the importance of compliance with their assigned regimen with an emphasis on correct use of study drug and the administration of and timing of doses.

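### One kit lasts about 30 days but the ±7-day windows allow longer intervals, so drug can run out before late Week 4, 8 or 12 visits, and before Week 24 only if unfinished units are collected

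*Protocol*

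**What the plan says.** Section 5.1 sets the dispensing rule. A double-blind kit is given at Day 1 and again at the four-weekly visits through Week 8; then: "subjects will receive 1 kit. At Week 12, subjects will receive 3 kits". Sections 6.2 and 6.3 repeat these numbers. Nothing is dispensed at the Week 16 and Week 20 contacts.

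On kit content, Section 5.3 says "each study drug kit, including the single-blind kit, and will consist of 2 units" and "each unit will contain either 120 sprays of study drug or placebo as necessary to maintain the blind". Section 5.2 makes 120 a minimum: "Once primed, study drug contains not less than 120 metered sprays".

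On use, Section 5.1 has the subject pick up unit 1, "administer 1 spray to the right nostril followed by 1 spray to the left nostril, and then to pick up the unit marked 2" and do the same again, at both the morning and the evening dose. Dosing is to be about every 12 hours throughout the study.

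On timing, the schedule gives Weeks 4, 8, 12 and 24 a window of ±7 days. Footnote a reads "If necessary, visits may be performed within the time window shown" and ties every visit back to Day 1, so shifts do not accumulate.

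On leftover drug, Section 5.7 says "subjects will be instructed to bring their partially used/empty study drug units back to the study site at each study visit", where the units are visually inspected. The schedule has a single dispense/collect row. Section 5.4 requires drug to be returned and accounted for, and Section 5.5 places return to the sponsor at the end of the study. No section says whether a part-used unit goes home again with the subject.

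On extra supply, Section 5.1, Section 6.5 and schedule footnote h describe one kit per IWRS Unscheduled Visit, only for a delayed end-of-study CT scan. Section 6.6 covers unscheduled assessments and does not mention dispensing.

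**The concern.** The plan asks for continuous twice-daily dosing, fixes the number of kits per visit, and permits visit intervals longer than those kits last. A subject inside every window can therefore be without drug in the days before a visit, and no written rule resupplies a late routine visit.

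Lost doses can change efficacy only in the active arms, so off-drug days would tend to shrink the difference from placebo. A supply gap is not among the intercurrent events in Section 9.3.2, so the affected values would enter the analysis as ordinary observations. The assessments at risk are those made at or close to a late visit: SNOT-22 (two-week recall) and PGIC at Week 4 and, depending on what happens to leftovers, possibly the Week 24 CT, which supplies the APOV co-primary endpoint.

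**Working it through.** **Inputs.** At least 120 sprays per unit once primed (Sections 5.2, 5.3). Two units per kit, used side by side (5.3). Two sprays per unit per dose and two doses a day (5.1). Kits 1, 1, 1 and 3 at Day 1, Week 4, Week 8 and Week 12 (5.1). Windows of ±7 days from Day 1 (schedule, footnote a). The protocol states no days-per-kit figure, so there is none to reproduce.

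**Days per kit.** 120 / (2 × 2) = 30 days; three kits = 90 days; all six kits = 180 days.

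**Nominal visits.** 28 days against 30, and 84 against 90: no shortfall.

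**Longest permitted intervals and worst gaps**, counting days from randomization. With leftovers kept, the gap is the latest visit day minus cumulative supply (30, 60, 90, 180). With units collected, it is the longest interval minus what was dispensed at its start.

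| Interval | Longest interval | Dispensed | Worst gap, leftovers kept | Worst gap, units collected |
|---|---|---|---|---|
| Day 1 to Week 4 | 35 − 0 = 35 | 30 | 35 − 30 = 5 | 35 − 30 = 5 |
| Week 4 to Week 8 | 63 − 21 = 42 | 30 | 63 − 60 = 3 | 42 − 30 = 12 |
| Week 8 to Week 12 | 91 − 49 = 42 | 30 | 91 − 90 = 1 | 42 − 30 = 12 |
| Week 12 to Week 24 | 175 − 77 = 98 | 90 | none (180 exceeds 175) | 98 − 90 = 8 |

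Enumerating all 15⁴ = 50,625 combinations of whole-day shifts confirms the leftovers-kept column: 5, 3, 1 and 0 days. If units are collected but only the later visit of each pair is 7 days late, the gaps are 5, 5, 5 and 1 days.

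The Week 4 gap does not depend on what happens to leftovers. No double-blind drug precedes the first kit, and the run-in kit is placebo.

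**Which endpoints are reached.**
- *Week 4 CSNS (co-primary).* Section 9.3.1 averages the 7 days before Day 28, inside the first 30 days. Covered either way.
- *Week 4 SNOT-22 and PGIC.* Done at the visit, so exposed if the visit falls on about Days 31 to 35.
- *Week 8 and Week 12 diary averages.* If these end at nominal Days 56 and 84 (an assumption; Section 3.2.1.3 says only the 7 days before each time point), retained leftovers cover them (60 and 90 days). If units are collected, a Week 4 visit on Day 21 gives a kit lasting to Day 51, which is 5 days short of Day 56.
- *Week 24 CT (APOV co-primary).* Exposed only if units are collected and the Week 12 to 24 interval exceeds 90 days. The CT is done on or before the visit day (Section 6), so 8 days is an upper bound.

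**Sensitivity to priming.** If the 7 priming sprays came out of the 120, which Section 5.2 contradicts, a kit would last 113 / 4 = 28.25 days. Worst gaps would be 6.75, 6.5, 6.25 and 5.5 days with leftovers kept, and 6.75, 13.75, 13.75 and 13.25 days with units collected.

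**The case against.** The strongest reply is that the serious consequence depends on units being taken away at each visit, and the protocol never says so. Section 5.7 gives inspection as what happens when units are brought in. Section 6.2 has subjects bring kits and diary together, and the diary plainly goes home again. Section 5.5 puts return to the sponsor at the end of the study. The Visit 1 mark in the dispense/collect row is footnoted as dispensing only, so a mark there does not prove collection. This stands. A reader might infer that subjects who follow the protocol run out before Week 24, but if leftovers are kept, 180 days of drug always reaches Day 175. The schedule row and Section 5.4 lean towards collection without settling it.

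The larger gaps are also extremes. The 12- and 8-day figures need collection and consecutive visits at opposite ends of their windows. A reader could string together visits on Days 21, 63, 77 and 175 and arrive at 12 + 8 = 20 of 175 days (11%) without drug. That is one constructed sequence under collection and should not be read as an expected loss. Windows are to be used only when necessary, 120 sprays is a minimum, and missed doses stretch supply.

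Finally, it can be said that nothing contradicts anything, because no days-per-kit figure is stated and IWRS manages supplies generally (Section 3.3). This does not stand. The days per kit follow directly from stated quantities, and extra dispensing is written only for a delayed end-of-study CT. For a late Week 4 visit the written rules cannot all be met.

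**Conclusion.** The stated supply rule does not cover the permitted visit windows. Whatever happens to leftovers, drug can run out up to about 5 days before a Week 4 visit held after about Day 30. With all leftovers kept, late Week 8 and Week 12 visits can still be 3 and 1 days short, and Week 24 is always covered. If unfinished units are collected, the worst gaps are 5, 12, 12 and 8 days, and APOV at Week 24 could be touched. The documents leave that condition open.

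The result assumes 30 days per kit, full compliance and use of the windows to their limits. The direction of effect, dilution of active versus placebo, is reasoned; its size cannot be estimated from the documents, which do not show how often visits run late. The documents support neither a general claim that the co-primary results are compromised nor any effect on the Week 4 CSNS. What is certain is limited to secondary assessments at late visits. The change is still worth making because it is cheap and removes a possible exposure of a co-primary endpoint.

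**What to change.** Reconcile three sets of provisions so that drug in hand reaches the latest permitted date of the next visit: the dispensing rule (Sections 5.1, 6.2, 6.3), the handling of returned units (the dispense/collect row, Sections 5.4 and 5.7), and the visit windows. This can be done without touching dose, regimen or windows:

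- State that unfinished units stay with the subject until the next kit is needed. By the arithmetic above, this alone removes any Week 24 gap.
- Extend the existing IWRS Unscheduled Visit dispensing to any visit that will fall beyond the days supplied. The late Week 4 gap needs this, because no leftovers precede it.

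The cost is one protocol sentence, an IWRS setting and a few extra kits for late visits. Larger standing kit allotments for everyone are not needed. SAP Section 4.3 reports that the blinded interim analysis, planned for when at least half of subjects had reached Week 24, has taken place, so the change helps only subjects with visits still to come. For the others, comparing dispensing dates with visit dates would show how many intervals exceeded the supply.

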5.2 Clinical Supplies

The fluticasone propionate suspension formulation is a milky, pale, white liquid contained within an EDS. Each actuation delivers 93 µg of fluticasone propionate through the sealing nosepiece. Once primed, study drug contains not less than 120 metered sprays.

The placebo used in this investigation will be a formulation identical to the active with the omission of the drug substance fluticasone propionate and will be delivered by an identical delivery system to the active formulation.

5.3 Packaging and Labeling

The practice EDS is to be used only at Visit 1 (Screening) to confirm a subject's ability to use the EDS and will be packaged in a demonstrator model EDS kit containing 1 unit.

Study drug will be packaged identically for each unit of study drug and placebo, and each study drug kit, including the single-blind kit, and will consist of 2 units, 1 marked "1" and 1 marked "2"; each unit will contain either 120 sprays of study drug or placebo as necessary to maintain the blind.

Labeling will contain all information required by local regulations.

5.4 Dispensing and Return of Study Drug

The investigator or designee at each site will maintain accurate records of study drug, including to whom study drug has been dispensed, dates and quantity. All study drug should be returned to storage, and accounted for, including dates and quantity (subject by subject accounting). Any study drug unit accidentally or deliberately destroyed will also be documented.

5.5 Storage and Reconciliation of Supplies

All study drug will be supplied by the Sponsor and should be stored securely in a locked facility.

All study drug must be stored at room temperature (between 15°C and 25°C: 59°F and 77°F, with excursions permitted from 15°C and 30°C: 59°F and 86°F). Avoid exposure to extreme heat, cold or light. Shake study drug before each use. Keep all study drug in the manufacturer's packaging.

The shelf life of the product will be supported by ongoing stability studies.

All used and unused study drug units will be returned to the Sponsor or designee at the end of the study. Reasons for departure from the expected dispensing or return of study drug units must be recorded.

5.6 Concomitant Medication

All pre-study medications used within 1 month before Visit 1 (Screening) must be recorded in the CRF. For subjects with comorbid asthma or COPD, pre-study inhaled steroid (beclomethasone or equivalent) use within the 3 months before Visit 1 (Screening) must be recorded in the CRF.

Concomitant medications include all medications and other treatments taken by the subject during the study, including those treatments initiated prior to the start of the study. All concomitant medications must be recorded on the CRF.

5.6.1 Allowed Concomitant Medications

In subjects with comorbid asthma at study entry (ie, Visit 1 [Screening]), inhaled corticosteroid use must be limited to stable doses of ≤ 1000 $\mu\text{g}/\text{day}$ of beclomethasone HFA (or equivalent; see [Attachment 1](#)). Subjects must be on a stable dose for at least 3 months before Visit 1 (Screening) with plans to continue use throughout the study.

Other concomitant medications allowed include:

- Antibiotic medications for bacterial infections that develop during the study.
- Intranasal saline spray with the exception of use within 2 hours before or after study drug administration.
- Saline lavage *only* for those subjects regularly using it before study entry; subjects may not initiate use during the study (saline lavage must not be performed within 2 hours before or after study drug administration or within 48 hours prior to a CT scan)
- Intranasal antibiotics in conjunction with lavage, but must not be given within 2 hours before or after study drug administration.
- Stable doses (within 2 weeks of Visit 1 [Screening]) of leukotriene receptor antagonists, beta-blockers, and neuroleptics.
- Low to medium strength topical corticosteroids for dermatologic purposes
- Montelukast sodium (Singulair) for subjects using it before study entry provided its use is continued throughout the study.
- Aspirin use for desensitization only for those subjects who were receiving therapy prior to study entry and whose symptoms were stable.
- Oxymetazoline or other topical nasal decongestant as part of the nasal examination only but may not be used within 24 hours of CT scan being performed

5.6.2 Rescue Medication

Use of rescue medication for CRS symptoms is not allowed during the single-blind run-in or before the Week 4 visit of the double-blind treatment phase. Subjects will be allowed to use over-the-counter non-sedating antihistamine (eg, cetirizine, levocetirizine, desloratadine) at the label-recommended, usual dose per day as rescue medication following the Week 4 visit.

Other concomitant medications are allowed, if not specially listed below as prohibited.

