3.2 Endpoints

3.2.1 Efficacy Endpoints

3.2.1.1 Primary Endpoint

Co-primary Endpoints

- change from baseline to the end of Week 4 in average instantaneous AM scores (evaluation of symptom severity immediately preceding the time of scoring) of:
 - nasal congestion
 - nasal discharge (anterior and/or posterior)
 - facial pain/pressure sensation

The baseline CSNS is the average of the total instantaneous AM scores over the last 7 days of the single-blind run-in period, and the end of Week 4, scores are averaged over the 7 days before Week 4.

- change from baseline to Week 24/ET in the APOV in the ethmoid and maxillary sinuses.

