11. subjects with comorbid asthma or COPD must be stable with no exacerbations (eg, no emergency room visits, hospitalizations, or oral or parenteral steroid use) within the 3 months before Visit 1 (Screening). Inhaled corticosteroid use must be limited to stable doses of no

- more than 1,000 µg/day of beclomethasone (or equivalent, see [Attachment 1](#)) for at least 3 months before Visit 1 (Screening) with plans to continue use throughout the study.
12. Subjects with aspirin-exacerbated respiratory disease, who have undergone aspirin desensitization and are receiving daily aspirin therapy, must be receiving therapy for at least 6 months prior to Visit 1.
 13. must be able to cease treatment with intranasal steroids, inhaled corticosteroids (except permitted doses listed above for asthma and COPD) at the screening visit
 14. must be able to cease treatment with oral and nasal decongestants and antihistamines at Visit 1 (Screening)
 15. must be able to use the EDS correctly; all subjects will be required to demonstrate correct use of the practice EDS at Visit 1 (Screening), see [Section 6.1](#)
 16. must be capable, in the opinion of the investigator, of providing informed consent to participate in the study. Subjects must sign an informed consent document indicating that they understand the purpose of and procedures required for the study and are willing to participate in the study.

4.2 Exclusion Criteria:

Potential subjects who meet any of the following criteria will be excluded from entering this study:

1. women who are pregnant or lactating
2. inability to have each nasal cavity examined for any reason, including nasal septum deviation
3. inability to achieve bilateral nasal airflow
4. is currently taking XHANCE
5. have previously used XHANCE for more than 1 month and did not achieve an adequate symptomatic response
6. the nasal/sinus anatomy prevents the accurate assessment of sinus volume via CT scan
7. history of sinus or nasal surgery within 6 months before Visit 1 or has not healed from a prior sinus or nasal surgery

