5.6.3 Prohibited Medications

- Exposure to any glucocorticoid treatment with potential for systemic effects (eg, oral or parenteral steroids, high dose topical steroids) within 1 month before the screening visit through completion of the study; except as noted for subjects with comorbid asthma or COPD.
- Any systemic, inhaled, intranasal and topical corticosteroids (except low to medium strength topical corticosteroids as noted above)
- XHANCE (fluticasone propionate), mepolizumab, reslizumab, dupilumab, omalizumab, or benralizumab
- Use of strong cytochrome P450 3A4 (CYP3A4) inhibitors (eg, ritonavir, atazanavir, clarithromycin, indinavir, itraconazole, nefazodone, nelfinavir, saquinavir,

ketoconazole, telithromycin, conivaptan, lopinavir, voriconazole, cobicistat) because increased systemic corticosteroid AEs may occur

- Steroid Eluting Sinus Implant (Propel[®], SINUVA[®])

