9.3.1 Co-primary Endpoints

- Change from baseline to the end of Week 4 in 7-day average instantaneous AM CSNS (evaluation of symptom severity immediately preceding the time of scoring)
 - nasal congestion
 - nasal discharge (anterior and/or posterior)
 - facial pain or pressure sensation

The baseline CSNS will be the average of the CSNS over the last 7 days of the placebo run-in period prior to randomization. The CSNS at Week 4 will be the average of the CSNS over the 7 days prior to Day 28.

AND

- The change from baseline to Week 24/ET in the APOV in the ethmoid and maxillary sinuses (APOV is the average percentage of volume opacified across both maxillary and ethmoid sinuses (all 4 sinuses) at each timepoint)

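### Do antihistamine and decongestant rules that do not line up, with rescue able to open before Day 28, undermine the Week 4 CSNS comparison?

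*Protocol*

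**What the plan says.** **Entry.** Protocol section 4.1, criterion 14: a subject "must be able to cease treatment with oral and nasal decongestants and antihistamines at Visit 1 (Screening". The synopsis repeats it. It is an entry condition and sets no duration.

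**Rescue.** Section 5.6.2: "Use of rescue medication for CRS symptoms is not allowed during the single-blind run-in or before the Week 4 visit". Sections 6.1, 6.2 and 6.3 repeat the bar with the same restriction to CRS symptoms. After the Week 4 visit an over-the-counter non-sedating antihistamine is permitted. Section 5.6.2 then closes with "Other concomitant medications are allowed, if not specially listed below as prohibited".

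**Prohibited and allowed drugs.** Section 5.6.3 carries the steroid entry rule forward ("Any systemic, inhaled, intranasal and topical corticosteroids (except low to medium strength topical corticosteroids as noted above") but names no antihistamine or decongestant. Section 5.6.1 allows "Oxymetazoline or other topical nasal decongestant as part of the nasal examination only" and does not mention oral decongestants.

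**Timing.** The Week 4 visit has a window of ±7 days. Footnote a of the Schedule of Study Procedures says "If necessary, visits may be performed within the time window shown". The endpoint is tied to a study day: section 9.3.1 has "The CSNS at Week 4 will be the average of the CSNS over the 7 days prior to Day 28", and section 3.2.1.1 says "scores are averaged over the 7 days before Week 4".

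**Estimand.** Section 9.3.2 lists three intercurrent events: systemic corticosteroids for CRS, nasal surgery and treatment discontinuation. Antihistamine, decongestant and rescue use are not among them, nor are they in SAP Table 5.1. SAP section 2 refers data handling to the CS-3205 SAP, which is not among the documents reviewed.

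**The concern.** Week 4 CSNS for the 372 µg dose is a co-primary endpoint, and no key secondary is tested unless both co-primaries succeed. The four Week 4 symptom endpoints come from the same morning diary. That diary grades congestion and discharge by severity, not cause, so a tablet taken for allergy or a cold can lower a CRS score.

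Two sites could read the text differently. One, following criterion 14, would keep subjects off these drugs and log any use as a deviation. The other, following sections 5.6.2 and 5.6.3, would accept non-CRS use as allowed. An early Week 4 visit would also open permitted rescue on mornings that still count towards the endpoint. If placebo subjects used more, the active-minus-placebo difference would shrink and power would fall.

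**Working it through.** **1. The plan's own power.** Inputs from Protocol section 9.1: 70 per arm, difference 0.9, SD 1.7, two-sided 5%.

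- Standard error = 1.7 × √(2/70) = 0.287
- 0.9 / 0.287 = 3.13
- Normal approximation: Φ(3.13 − 1.96) = 87.9%. Noncentral t with 138 df: 87.5%.

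The stated 88% reproduces.

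**2. What the text leaves open.**

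| Use | Before the Week 4 visit | After it |
|---|---|---|
| Antihistamine or oral decongestant as rescue for CRS symptoms | Barred (5.6.2, 6.1–6.3) | Non-sedating antihistamine allowed |
| Topical nasal decongestant | Nasal examination only (5.6.1) | Same |
| Antihistamine or oral decongestant for another reason | No explicit rule; the default sentence in 5.6.2 allows it | Same |

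Only the last row, and the first row after an early visit, reach the scored mornings.

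**3. Early visits.** Take the scored mornings as Days 21–27, with the morning score recorded before that day's visit. A visit on day d then exposes max(0, 27 − d) mornings.

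- Earliest visit on Day 21 or 22 (depending on whether Week 4 is counted as Day 28 or Day 29): 6 or 5 of 7 mornings.
- Visits spread evenly over ±7 days: 21/15 = 1.4 mornings (20.0%) or 15/15 = 1.0 morning (14.3%). This is pessimistic, since the window is for use only when needed.
- Visits spread evenly over ±3 days: 3/7 = 0.43 mornings (6.1%) or 1/7 = 0.14 mornings (2.0%).

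**4. Bias at Week 4.** Bias = excess proportion using on placebo × CSNS effect per user. The documents give neither term, so these are assumed ranges, not estimates.

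- Non-CRS use, excess 0 to 0.10, effect 0.5 to 1.0: bias from 0 to 0.10 × 1.0 = 0.10, or 0 to 11% of 0.9. At the extreme (difference 0.80) the t-based power would be 78.9%.
- Early rescue, excess 0.20 to 0.30: bias from 0.0204 × 0.20 × 0.5 = 0.002 to 0.20 × 0.30 × 1.0 = 0.06.

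The extreme in the first line needs a cold or allergy tablet to move CSNS by 1.0, more than the 0.9 planned for the study drug. It also needs a 10-point imbalance in use for reasons other than CRS. Nothing in the documents supports either.

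**5. Baseline.** The baseline window precedes randomisation, so use there cannot differ systematically between arms. It can add noise but not treatment bias.

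**6. Noise.** With 20% use in both arms, adding the between-subject variance gives SD = √(1.7² + 0.20 × 0.80 × effect²), which is 1.71 for an effect of 0.5 and 1.75 for 1.0. This probably counts the noise twice. Protocol section 9.1 takes its updated SD from the blinded CS-3205 interim, and SAP section 2 calls that study identical in design apart from polyp status. SAP section 4.3 reports that this study's own blinded variance check led to no increase in sample size.

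**The case for a change.** The strongest case for acting is that the mismatch is in the protocol itself, so no SAP can cure it. The steroid entry criterion has a matching on-study prohibition and criterion 14 does not. The bar on rescue turns on the stated reason for taking a tablet, which the diary cannot check. The estimand text is silent on these drugs. The remedy would be cheap: a reconciling edit, a sentence stating that observed scores are used, and a count by arm.

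Part of this stands. Section 5.6 has no explicit rule for non-CRS use before the Week 4 visit, and the visit-keyed opening of rescue does not match the Day 28 window.

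The rest does not lead to a change:

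- Criterion 14 concerns ability to stop at entry. What is missing is an on-study rule; there are not two rules giving opposite orders.
- The closing sentence of section 5.6.2 follows directly on the one that opens antihistamines after Week 4. Its opening word can fairly be read as meaning drugs other than those, which narrows the gap further.
- The suggested estimand sentence would record what already happens. Note 6 to SAP Table 5.1 uses the Week 4 value for subjects who reach Week 4, and these drugs trigger no composite score.
- All concomitant medication goes on the CRF (5.6) and is summarised by drug class (9.9.2). Deviations go in the study report (13.2.2), and the per-protocol set, fixed before unblinding, gives a sensitivity analysis (9.2.4).
- The interim was planned for when at least 75% of subjects had reached Week 4, and SAP section 4.3 reports it as done. An edit now would alter the conduct of few subjects.

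**Conclusion.** No change to the plan follows. This is a gap in wording, and following the text as written gives a valid treatment-policy comparison at Week 4. Under the null, with no drug effect on symptoms, there is no symptom-driven reason for use to differ by arm. If the drug works, the likelier imbalance is more use on placebo, which dilutes the difference. The risk is therefore to power, and its size cannot be derived from the documents. The 0 to 0.10 range rests wholly on assumed rates and effects, and the power figure at its extreme should not be cited as an expected loss.

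If the protocol is edited for other reasons, the sponsor should reconcile criterion 14 with sections 5.6.1 to 5.6.3, and the opening of rescue in sections 5.6.2 and 6.3 with the scoring window in sections 3.2.1.1 and 9.3.1. Which medication rule is right is not a matter for this review. A count by arm of such use in the two 7-day windows could be drawn from data already collected, if a reader of the results wants it. The primary analysis, the stated 88% power and the testing order are unaffected. The conclusion assumes that the CS-3205 SAP contains no rule setting aside scores after such use; that document could not be checked.
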